#### **9.5.3.1.1.4 Unexpected Adverse Event Definition**

An AE or suspected adverse reaction is considered unexpected if it is not listed in the Reference Safety Information section of the Investigator's Brochure or is not listed with the specificity or severity that has been observed. Unexpected, as used in this definition, also refers to AEs or suspected adverse reactions that are mentioned in the Reference Safety Information as occurring with a class of drugs or as anticipated from the pharmacological properties of the drug but are not specifically mentioned as occurring with the particular drug under investigation.

#### **9.5.3.1.1.5 Adverse Events of Special Interest**

Based on previous clinical experience in TFD, the following will be AESIs for this trial:

- Infusion reactions
- Hyperglycemia
- Muscle spasms
- Hearing impairment
- New onset inflammatory bowel disease and exacerbation of inflammatory bowel disease

#### **Risk of Hypersensitivity (Infusion-related events)**

- Administration of mAbs may cause infusion-related symptoms, such as fever, chills, hypotension, shortness of breath, skin rash and headache. Such reactions typically occur

during or shortly after the infusion of mAbs and are usually associated with the first infusion. Their incidence and severity typically decrease with subsequent infusions. Severe infusion-related reactions might be clinically indistinguishable from anaphylactic reactions.

- Infusion-related events observed with teprotumumab to date have not been anaphylactic in nature. However, because of the protein nature of teprotumumab and the potential for infusion-related reactions and hypersensitivity reactions, teprotumumab should be administered in a setting with emergency equipment and staff who are trained to monitor medical situations and respond to emergencies. For the first 3 infusions, patients should be monitored for any events during infusion and for 60 minutes after completion of infusion. For subsequent infusions (the fourth dose and beyond), patients who have not previously experienced an infusion reaction should be monitored during the infusion and for at least 30 minutes after the infusion.
- Patients who exhibit immediate hypersensitivity reactions or infusion-related reactions during an infusion of teprotumumab should have the infusion interrupted or the infusion rate slowed. Symptomatic treatment, e.g., antipyretics, antihistamines and/or corticosteroids, oxygen, beta agonists and IV fluids, should be administered to the patient. Following an immediate hypersensitivity reaction or infusion-associated reaction, vital signs (temperature, blood pressure, pulse and respiratory rate) will be monitored every 5 minutes until stable, and then every 15 minutes for 2 additional determinations. The infusion may be restarted upon complete resolution of symptoms except in the case of patients who experience an anaphylactic reaction of life-threatening intensity; these patients should be removed from the trial.
- In general, the decision to keep a patient on trial treatment with teprotumumab should take into consideration potential risks and benefits to the patient. Prior to future infusions of teprotumumab, these patients may be premedicated with IV diphenhydramine 1 to 1.25 mg/kg (maximum 50 mg), IV ranitidine 50 mg, IV famotidine 0.5 mg/kg, IV dexamethasone 0.4 mg/kg (maximum 20 mg) and/or acetaminophen 500 mg. In addition, all future infusions should be administered over 90 minutes. Vital signs should be taken every 15 minutes during the infusion through 60 minutes after infusion completion.
- Patients who experience delayed-type hypersensitivity reactions (e.g., skin rash) may remain in the trial at the discretion of the Investigator and, prior to all future infusions of teprotumumab, may be premedicated with the above medications (diphenhydramine, ranitidine, famotidine, dexamethasone and acetaminophen). However, if a rash worsens

following repeated dosing or other signs of serum sickness (e.g., delayed fever, myalgias, arthralgias) are present, trial drug dosing will be permanently discontinued.

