#### 9.3.3.1 Discontinuation of Patients from Treatment

The primary reason for discontinuation from trial drug should be recorded on the eCRF using 1 of the following categories:

- AE. The patient experiences an AE that imposes an unacceptable risk to the patient's health, or the patient is unwilling to continue because of an AE. Patients who discontinue trial drug due to an AE will remain in the trial unless they withdraw from the trial for another reason. AEs requiring permanent trial drug discontinuation per the protocol include:
  - A drug-related anaphylactic reaction as defined by Sampson criteria (see Appendix 17.3 for clinical criteria).
  - Diagnosed or suspected inflammatory bowel disease (e.g., diarrhea with or without blood or rectal bleeding associated with abdominal pain or cramping/colic, urgency, tenesmus or incontinence for more than 4 weeks without a confirmed alternative diagnosis OR endoscopic or radiologic evidence of enteritis/colitis without a confirmed alternative diagnosis).
- Lack of Efficacy. Discontinuation of trial drug due to lack of efficacy is at the discretion of the Investigator or patient and may occur if the Investigator determines that trial drug administration is not benefiting the patient. Patients who discontinue trial drug due to

lack of efficacy will remain in the trial unless they withdraw from the trial for another reason.

- Lost to Follow-up. The patient does not return to the clinic for scheduled assessments and does not respond to the site's attempts to contact the patient.
- Withdrawal by Patient/Guardian. The patient wishes to withdraw from trial drug. The clinical site should attempt to determine the underlying reason for the voluntary withdrawal and document it on the eCRF
- Trial Terminated by Sponsor. The Sponsor, IRB or regulatory agency terminates the trial.
- Pregnancy.
- Death.
- Completed. The patient completed treatment.

Patients who prematurely discontinue trial drug prior to Week 21 of the double-masked Treatment Period or who enter the open-label Treatment Period and discontinue trial drug prior to Week 45 of the open-label Treatment Period will return to the clinic, undergo the scheduled End-of-Treatment assessments (with the exception of the **CCI** [REDACTED]

**CCI** [REDACTED] and enter the Follow-up Period. Patients who discontinue due to an AE should be followed until resolution or stabilization of the AE, or an adequate explanation for the event is obtained.

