#### 9.3.3.2 Removal of Patients from the Trial

The primary reason for discontinuation from the trial should be recorded on the eCRF using 1 of the following categories:

- Lost to Follow-up. The patient does not return to the clinic for scheduled assessments and does not respond to the site's attempts to contact the patient.
- Withdrawal by Patient/Guardian. The patient wishes to withdraw from the trial. The clinical site should attempt to determine the underlying reason for the voluntary withdrawal and document it on the eCRF.
- Trial Terminated by Sponsor. The Sponsor, IRB or regulatory agency terminates the trial.
- Death.
- Completed. The patient completed the trial.

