#### **9.4.6.3.2 Dose Modifications, Interruptions and Delays**

All dosing instructions are applicable for TEPEZZA and placebo administration.

Patients will be evaluated for safety throughout the trial. For the first 3 infusions, patients will be monitored for any AEs during the infusion and for 60 minutes after completion of the infusion for immediate infusion-associated events (e.g., transient increase in blood pressure, feeling hot, tachycardia, dyspnea, headache and muscular pain) and delayed infusion-associated events (e.g., rash). For subsequent infusions (if no previous infusion reactions), patients will be monitored during and for at least 30 minutes after completion of the infusion.

If immediate infusion-associated events are noted, the infusion rate may be slowed or interrupted and symptomatic treatment (e.g., antipyretics, antihistamines, beta-agonists, glucocorticoids, oxygen, IV fluid) may be administered, as necessary. Vital signs (temperature, blood pressure, pulse and respiratory rate) will be monitored every 5 minutes until stable and then every 15 minutes for 2 additional determinations. The infusion may be restarted upon complete resolution of symptoms; however, TEPEZZA dosing will be permanently discontinued if the event is an anaphylactic reaction.

If delayed infusion-associated events are noted, patients may continue dosing at the Investigator's discretion; however, if a rash worsens following repeated dosing or other signs of serum sickness (e.g., delayed fever, myalgias, arthralgias) are present, TEPEZZA dosing will be permanently discontinued. If an infusion-associated event is experienced after patients are discharged from the site, the Investigator is to be contacted as soon as possible.

Following the appearance of either immediate or delayed infusion-associated events, patients who receive subsequent doses may be pre-treated with diphenhydramine (1 to 1.25 mg/kg IV; maximum of 50 mg), ranitidine (50 mg IV), famotidine (0.5 mg/kg IV), dexamethasone (0.4 mg/kg IV; maximum of 20 mg) and/or acetaminophen (500 mg). All subsequent infusions will be administered over approximately 90 minutes (but not less than 80 minutes) with vital signs monitored every 15 minutes from the start of the infusion through 60 minutes after completion of the infusion.

In general, the decision to continue dosing should take into consideration the potential benefit and risk to a patient.

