### 17.3 Sampson Criteria for Anaphylactic Reaction

**Anaphylaxis is highly likely when any one of the following 3 criteria are fulfilled:**

[figure not shown]
1. Acute onset of an illness (minutes to several hours) with involvement of the skin, mucosal tissue, or both (eg, generalized hives, pruritus or flushing, swollen lips-tongue-uvula)  

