**AND AT LEAST ONE OF THE FOLLOWING**
  - a. Respiratory compromise (eg, dyspnea, wheeze-bronchospasm, stridor, reduced PEF, hypoxemia)
  - b. Reduced BP or associated symptoms of end-organ dysfunction (eg, hypotonia [collapse], syncope, incontinence)
2. Two or more of the following that occur rapidly after exposure to a *likely allergen for that patient* (minutes to several hours):
  - a. Involvement of the skin-mucosal tissue (eg, generalized hives, itch-flush, swollen lips-tongue-uvula)
  - b. Respiratory compromise (eg, dyspnea, wheeze-bronchospasm, stridor, reduced PEF, hypoxemia)
  - c. Reduced BP or associated symptoms (eg, hypotonia [collapse], syncope, incontinence)
  - d. Persistent gastrointestinal symptoms (eg, crampy abdominal pain, vomiting)
3. Reduced BP after exposure to *known allergen for that patient* (minutes to several hours):
  - a. Infants and children: low systolic BP (age specific) or greater than 30% decrease in systolic BP\*
  - b. Adults: systolic BP of less than 90 mm Hg or greater than 30% decrease from that person's baseline

PEF: Peak expiratory flow; BP: blood pressure.

\*Low systolic blood pressure for children is defined as less than 70 mm Hg from 1 month to 1 year, less than  $(70 \text{ mm Hg} + [1 \times \text{age}])$  from 1 to 10 years, and less than 90 mm Hg from 11 to 17 years.

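### The AESI section allows an infusion restart after anaphylaxis that is not life-threatening, which two other sections rule out, and it conflicts with 9.3.3.1 on whether the patient stays in the trial

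*Protocol*

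**What the plan says.** Three places in the current protocol govern dosing after an anaphylactic reaction.

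- **9.5.3.1.1.5, Risk of Hypersensitivity.** The infusion may restart when symptoms have completely resolved, "except in the case of patients who experience an anaphylactic reaction of life-threatening intensity; these patients should be removed from the trial".
- **9.4.6.3.2, Dose Modifications, Interruptions and Delays.** "The infusion may be restarted upon complete resolution of symptoms; however, TEPEZZA dosing will be permanently discontinued if the event is an anaphylactic reaction". The section applies its dosing instructions to both arms.
- **9.3.3.1, Discontinuation of Patients from Treatment.** The adverse events that require a permanent stop include "A drug-related anaphylactic reaction as defined by Sampson criteria".

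On what happens to the patient afterwards, 9.3.3.1 says: "Patients who discontinue trial drug due to an AE will remain in the trial unless they withdraw from the trial for another reason". Section 9.3.3.2 covers leaving the trial itself: "The primary reason for discontinuation from the trial should be recorded on the eCRF using 1 of the following categories". It then lists five: lost to follow-up, withdrawal by patient or guardian, termination by the sponsor, death, and completion.

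Appendix 17.3 supplies the definition of anaphylaxis: "Anaphylaxis is highly likely when any one of the following 3 criteria are fulfilled".

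**The concern.** The sections give different instructions for the same event. The person most likely to consult the AESI text is an investigator managing a reaction, and that text goes on to describe premedication and slower rates for later infusions. Read alone, it is a complete route back to dosing. It also warns that "Severe infusion-related reactions might be clinically indistinguishable from anaphylactic reactions", yet it gives no definition to decide by and does not cite Appendix 17.3.

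The first stake is patient safety: re-exposure after anaphylaxis. The second is consistent conduct. If the patient is removed from the trial, a site may be unsure whether the premature-withdrawal visit (Schedule of Assessments, footnote 3) and the Follow-up Period still apply, and it has no fitting exit reason to record.

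**Working it through.** No arithmetic applies, so the check sets the provisions side by side.

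**Step 1: what each section requires**

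| Event during infusion | 9.5.3.1.1.5 | 9.4.6.3.2 | 9.3.3.1 |
|---|---|---|---|
| Reaction that is not anaphylaxis | Restart allowed after resolution | Restart allowed after resolution | Not on the mandatory-stop list |
| Anaphylaxis, not life-threatening | Restart allowed after resolution | Permanent stop | Permanent stop if drug-related and Sampson-defined; stays in trial |
| Anaphylaxis, life-threatening | No restart; removed from trial | Permanent stop | Permanent stop if drug-related and Sampson-defined; stays in trial |

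The sections agree in the first row. In the second they conflict on restarting. In the third they agree that drug stops but conflict on trial status.

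**Step 2: whether the second row can occur.** Section 9.5.3.1.3 ties life-threatening intensity to Grade 4, separate from mild, moderate and severe. If the AESI wording carries that meaning, a Grade 3 anaphylactic reaction falls outside its exception. The Sampson criteria use no grade, and any one of the three is enough. Criterion 2 asks for "Two or more of the following that occur rapidly after exposure" to a likely allergen; widespread hives with persistent vomiting would satisfy it. Criterion 1 can be met by an acute skin reaction with dyspnea. Neither combination requires an immediate threat to life, so the gap is real.

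**Step 3: whether any text sets precedence.** The synopsis and Sections 9.1 and 9.4.1 refer to 9.4.6.3.2 for dose handling. Within 9.5.3.1.1.5, the paragraph on severe diabetic complications says that infusion reactions are also covered there. None of these says that 9.4.6.3.2 overrides the AESI text.

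**Step 4: trial status.** Of the five exit reasons in 9.3.3.2, 0 cover an adverse event or an investigator decision. Removal also runs against SAP 9.1, which uses a treatment policy strategy for the continuous endpoints and encourages patients who stop treatment to stay.

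**The case against.** The strongest reply is that the dosing rules can all be obeyed at once. The AESI sentence only permits a restart, whereas 9.4.6.3.2 is mandatory. A site that stops drug after every anaphylactic reaction breaches nothing, and the AESI section itself points to 9.4.6.3.2. This is correct and softens the conflict. It protects only a site that reads both sections and takes the stricter rule; one acting on the AESI text as written would breach 9.4.6.3.2.

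Section 9.3.3.1 is also narrower than 9.4.6.3.2, being confined to drug-related, Sampson-defined reactions. That limit stands, but 9.4.6.3.2 has no such limit, so the conflict remains without 9.3.3.1.

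On removal, several points have force:

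- Nearby text sometimes speaks of the trial when it means dosing, so the AESI sentence may intend only that drug stops. Yet the same section refers to study treatment when discussing severe diabetic complications and profound hearing loss, so the loose reading is not secure.
- Section 9.3.3 lets the investigator end a patient's participation in the patient's interest. That is a case-by-case power, not a rule.
- The missing exit reason also affects removals under 9.3.3, so it is partly a separate gap in the form.
- The premature-withdrawal visit is triggered by stopping drug, and 9.5.3.1.5 requires serious events to be followed until resolved, stabilized or explained. Safety follow-up is therefore not lost; what remains is uncertainty about trial status and how to record it.

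**Conclusion.** The concern holds on current text and should be fixed. One section bars a restart only for life-threatening anaphylaxis. A second stops drug for any anaphylactic reaction, and a third does so for any drug-related, Sampson-defined one. The instruction to remove the patient contradicts 9.3.3.1 and has no matching reason in 9.3.3.2.

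The expected number of cases is small. The documents give no anaphylaxis rate, and 9.5.3.1.1.5 reports that infusion-related events so far have not been anaphylactic. The effect on the primary analysis should be negligible, and none is claimed. The importance lies in the possible harm from a single re-challenge. The restart conflict is the more serious part; the removal wording is secondary.

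The conclusion assumes that life-threatening intensity has its 9.5.3.1.3 meaning, and that a site may reasonably act on the AESI text without reconciling it with the other sections.

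**What to change.** Amend one sentence of 9.5.3.1.1.5:

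1. Delete the life-threatening qualifier, so that the exception covers any anaphylactic reaction, and cite the Sampson criteria in Appendix 17.3.
2. Replace removal from the trial with permanent discontinuation of trial drug. Where safe, keep the patient in the trial for End-of-Treatment and follow-up assessments.

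The stop then matches 9.4.6.3.2, which is not restricted to drug-related reactions, and the safety condition matches the welfare proviso in 9.1. No new exit reason is needed for these patients. The lack of one for investigator-decided removals under 9.3.3 remains a separate matter.

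The cost is one sentence, by amendment or clarification letter, with no added visits or procedures.

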#### **Risk of New Onset or Exacerbation of IBD**

- In Phase 2 TED01RV, 2 teprotumumab-treated patients with a history of IBD reported serious TEAEs (*Diarrhoea* in 1 patient and *Inflammatory bowel disease* in 1 patient) that led to discontinuation of trial drug. Based on these serious events and the fact that a placebo patient with Crohn's disease did not experience these types of events, patients with a history of IBD are either excluded from current trials or must be in clinical remission.
- Patients who experience progressive and persistent diarrhea or other IBD symptoms, such as bloody stools or abdominal pain, should undergo prompt evaluation to exclude new onset or exacerbation of preexisting IBD or other serious conditions. If possible, medications known to cause diarrhea, such as laxatives and magnesium shall be avoided. If new onset or exacerbation of IBD is suspected, teprotumumab shall be discontinued.

#### **Risk of Hyperglycemia**

- In nonclinical studies, there was no *in vitro* cross-reactivity of teprotumumab with the insulin receptor. Clinical trials in Active TED have shown a higher incidence of hyperglycemia in patients treated with teprotumumab compared to placebo. Patients with pre-existing diabetes mellitus (who were under appropriate glycemic control upon trial entry) or impaired glucose tolerance were more likely to experience an event of hyperglycemia after exposure to teprotumumab.

#### **Management of Patients with Diabetes Mellitus**

- Patients with known controlled diabetes mellitus are allowed to participate in trials with teprotumumab. HbA1c levels should be monitored every 6 weeks in these patients.
- Investigators are strongly encouraged to adjust their patients' diabetes management to maintain HbA1c levels ~8%. In the event a patient's HbA1c level rises to >8% while in the trial, the Investigator must assess the risk versus benefit for the patient to remain in the trial, discuss with sponsor's medical monitor or designee, and document the decision.

